6.14.1.1 Treatment Emergent Adverse Event (TEAE) Definition

- A TEAE is any untoward medical occurrence associated with the use of an investigational product or study procedure in a clinical study Participant, whether or not considered related to the study intervention.
- NOTE: A TEAE can therefore be any unfavorable and unintended sign (including an abnormal laboratory finding), symptom, or disease (new or exacerbated) temporally associated with the use of study intervention or procedure.
- An event that emerges during treatment, having been absent at pretreatment, or worsens relative to the pretreatment state, as defined in the E9 Guidance.
- The TEAE is not related to causality / drug relatedness. It may or may not be related to the drug but is considered a TEAE due to its appearance at or after the treatment has been administered.

Events Meeting the TEAE Definition

- Any abnormal laboratory test results (hematology, or clinical chemistry) or other safety assessments (e.g., ECG, radiological scans, vital signs measurements), including those that worsen from Baseline, considered clinically significant in the medical and scientific judgment of the investigator (i.e., not related to progression of underlying disease).
- Exacerbation of a chronic or intermittent pre-existing condition including either an increase in frequency and/or intensity of the condition.
- New conditions detected or diagnosed after study intervention administration even though it may have been present before the start of the study.
- Signs, symptoms, or the clinical sequelae of a suspected drug-drug interaction.
- Signs, symptoms, or the clinical sequelae of a suspected overdose of either study intervention or a concomitant medication. Overdose per se will not be reported as an TEAE/TESAE unless

QMD Ref: Worldwide-TMP-ST-005-7.0 Effective: 12Aug2019	Governing QMD: Worldwide-SOP-ST-001
Confidentiality Statement	

This document is the property of Worldwide Clinical Trials Inc. and may not be duplicated, copied, altered or removed from company without prior approval from Worldwide Quality Assurance or in compliance with Worldwide Standard Operating Procedures.

Worldwide Clinical Trials Controlled Quality Management Document			
 WORLDWIDE CLINICAL TRIALS	Sponsor:	Helixmith Co., Ltd.	
	Protocol Number:	VMALS-002-2b	
STATISTICAL ANALYSIS PLAN. PHASE 2-3-4			

it is an intentional overdose taken with possible suicidal/self-harming intent. Such overdoses should be reported regardless of sequelae.

Events NOT Meeting the TEAE Definition

- Any clinically significant abnormal laboratory findings or other abnormal safety assessments that are associated with the underlying disease, unless judged by the Investigator to be more severe than expected for the Participant's condition.
- The disease/disorder being studied or expected progression, signs, or symptoms of the disease/disorder being studied, unless more severe than expected for the Participant's condition.
- Medical or surgical procedure (e.g., endoscopy, appendectomy): the condition that leads to the procedure is the TEAE.
- Situations in which an untoward medical occurrence did not occur (social and/or convenience admission to a hospital).
- Anticipated day-to-day fluctuations of pre-existing disease(s) or condition(s) present or detected at the start of the study that do not worsen.

6.14.1.2 Treatment Emergent Serious Adverse Event (TESAE) Definition:

Any untoward medical occurrence that, at any dose:

- Results in death
- Is life-threatening

The term “life-threatening” in the definition of “serious” refers to an event in which the Participant was at risk of death at the time of the event. It does not refer to an event, which hypothetically might have caused death, if it were more severe.

- Requires inpatient hospitalization or prolongation of existing hospitalization
 - In general, hospitalization signifies that the Participant has been detained (usually involving at least an overnight stay) at the hospital or emergency ward for observation and/or treatment that would not have been appropriate in the physician's office or outpatient setting. Complications that occur during hospitalization are AEs. If a complication prolongs hospitalization or fulfills any other serious criteria, the event is serious. When in doubt as to whether “hospitalization” occurred or was necessary, the TEAE should be considered serious.
 - Hospitalization for elective treatment of a pre-existing condition that did not worsen from Baseline is not considered an SAE.

QMD Ref: Worldwide-TMP-ST-005-7.0 Effective: 12Aug2019	Governing QMD: Worldwide-SOP-ST-001
Confidentiality Statement	

This document is the property of Worldwide Clinical Trials Inc. and may not be duplicated, copied, altered or removed from company without prior approval from Worldwide Quality Assurance or in compliance with Worldwide Standard Operating Procedures.

Worldwide Clinical Trials Controlled Quality Management Document			
 WORLDWIDE CLINICAL TRIALS	Sponsor:	Helixmith Co., Ltd.	
	Protocol Number:	VMALS-002-2b	
STATISTICAL ANALYSIS PLAN. PHASE 2-3-4			

- d. Results in persistent disability/incapacity
 - The term “disability” means a substantial disruption of a person’s ability to conduct normal life functions.
 - This definition is not intended to include experiences of relatively minor medical significance such as uncomplicated headache, nausea, vomiting, diarrhea, influenza, and accidental trauma (e.g., sprained ankle), which may interfere with or prevent everyday life functions but do not constitute a substantial disruption.
- e. Is a congenital anomaly/birth defect
- f. Other situations:
 - Medical or scientific judgment should be exercised in deciding whether SAE reporting is appropriate in other situations such as important medical events that may not be immediately life-threatening or result in death or hospitalization but may jeopardize the Participant or may require medical or surgical intervention to prevent one of the other outcomes listed in the above definition. These events should usually be considered serious.
 - Examples of such events include invasive or malignant cancers; intensive treatment in an emergency room or at home for allergic bronchospasm, blood dyscrasias, or convulsions that do not result in hospitalization; or development of drug dependency or drug abuse.

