8.3.4. Adverse Events of Special Interest

Any of the AESIs that occur during the study, as described below, must be recorded as AESI and any of the AESI that meet the criteria for a serious event (Section 8.3) must be reported as a TESAE and identified as an AESI.

Categories of AESIs

There are two main categories of AESIs as presented below: 1) those considered to be related to the angiogenesis potential of Engensis, 2) other medical problems in this patient population, and 3) COVID-19 infections occurring in Participants during the study.

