9.3.1. Primary Endpoints

Safety analyses in this study will evaluate the safety profile of Engensis. The primary endpoints for safety are as follows:

- Incidence of TEAEs, TESAEs, and AESIs
- Incidence of clinically significant laboratory values

No formal statistical testing will be conducted for the safety analyses. All Participants in the Safety Population will be included in these analyses. For data analysis, Participants will be grouped by the treatment received during VMALS-002-2. All summaries will be derived from and based on available data. No imputation will be performed for missing values. All safety analyses will be made on the Safety Population.

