4 SAMPLE SIZE

The number of Participants in this study will be determined by the number who complete the Day 180 Visit in VMALS-002-2. The maximum potential Participants in VMALS-002-2b is 18, based on enrollment in VMALS-002-2.

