In this study the adverse events (AEs) will be presented from collected since Screening visit of VMALS-002-2 study. AEs that registered as not treatment emergent (not TEAEs) will be presented in a separate listing and will not be tabulated. TEAEs will be tabulated in similar manner as two sets: TEAEs started at date of signing of IC for this study or later and all TEAEs collected during both studies. All AEs from both studies will be united for presenting in listings.

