- Bulbar Disease: Participants may develop bulbar disease or worsening on bulbar disease during the study, manifested as challenges with dysarthria, facial weakness, impaired tongue pulsion or palate elevation, and impaired mastication and swallowing; all of these types of events that occur during the study will be considered AESIs.

COVID-19 Infections

A diagnosis of COVID-19 infection occurring in participants will be recorded as an AESI and their disposition during the trial following the diagnosis of the COVID-19 infection will be tracked.

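### The SAP's rule against tabulating non-TEAEs can keep AESIs judged to be expected ALS progression, mainly bulbar signs, out of the primary AESI incidence table

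*SAP*

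**What the plan says.** - **Endpoint.** Protocol 9.3.1 names "Incidence of TEAEs, TESAEs, and AESIs" as a primary endpoint, and SAP 3.1 frames it as Engensis compared with placebo.
- **AESI definition.** Protocol 8.3.4 states: "Any of the AESIs that occur during the study, as described below, must be recorded as AESI". Protocol 8.3.4.2 and SAP 6.14.1.3 give three ALS-type categories: pulmonary problems, rapidly progressing weakness with stated consequences, and new or worsening bulbar disease. For the bulbar category the SAP says "all of these types of events that occur during the study will be considered AESIs". None of the three asks whether the event was expected.
- **TEAE definition.** SAP 6.14.1.1 and protocol 10.2.1 both exclude "expected progression, signs, or symptoms of the disease/disorder being studied, unless more severe than expected" for the participant's condition. Protocol 8.3.9 also takes signs and symptoms of ALS out, while keeping other disease-related events in.
- **Tabulation.** SAP 6.14.1: "AEs that registered as not treatment emergent (not TEAEs) will be presented in a separate listing and will not be tabulated". It makes no exception for AESIs.
- **Output.** SAP 6.14.1.4 names one AESI table (14.3.1.9) and one AESI listing (16.2.7.2). It sends events registered as not TEAEs to Listing 16.2.7.7.

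**The concern.** AESIs and TEAEs are defined by different tests. The AESI test asks what kind of event occurred. The TEAE test also asks, for ALS manifestations, whether the event was worse than expected. If the AESI table is built only from TEAEs, the second test enters an endpoint whose definition does not contain it.

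The reported AESI incidence would then count only those ALS-type events that an investigator judged out of line with expected progression. A gradual worsening of bulbar function is easily called expected, so it is the kind of event most likely to be filtered out. Blinding should limit any difference between arms in that judgement, but it does not put the excluded events back. Two programmers could also produce different primary tables from the same data and each cite the SAP in support.

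**Working it through.** The documents state no figure to reproduce on this point. Protocol 9.3.1 says "No formal statistical testing will be conducted for the safety analyses", and neither document gives an expected AESI rate or arm sizes. The check is therefore a reading of the rules in sequence, with one piece of arithmetic on scale.

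**Following one event through the rules.** A participant has worsening dysarthria during the extension, and the investigator judges it to be in line with expected ALS progression.

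1. Is it an AESI? Yes. Worsening bulbar disease is included without an expectedness condition (protocol 8.3.4.2, SAP 6.14.1.3), and recording it as an AESI is mandatory (protocol 8.3.4).
2. Is it a TEAE? By timing, yes: SAP 6.14.1.1 treats an event as treatment-emergent because it appears at or after treatment. By the list of events not meeting the definition, no: expected progression is removed unless it is more severe than expected. Protocol 8.3.9 also points to no for a sign or symptom of ALS. The exclusion is the more specific rule.
3. If it is registered as not a TEAE, may it be tabulated? Under SAP 6.14.1, no. It goes to a listing.
4. Does anything restore it to Table 14.3.1.9? Nothing in SAP 6.14.1.3 or 6.14.1.4 says that the table counts AESIs that are not TEAEs.

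**Same steps for the other ALS-type categories.**

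- *Weakness.* The category requires rapid progression with consequences such as loss of self-care, decubitus ulcers or weight loss. That is a condition on speed and consequence, not on expectedness. Many such events would probably be judged worse than expected and so be TEAEs; some might not.
- *Pulmonary.* Pneumonia and aspiration can be read as disease-related events rather than signs or symptoms of ALS, in which case protocol 8.3.9 makes them TEAEs. The conflict is weakest here.

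**A parallel conflict for serious events.** Protocol 8.3.4 says that a serious AESI "must be reported as a TESAE and identified as an AESI", with no expectedness condition. Protocol 10.2.2 says that an event which is not a TEAE cannot be a TESAE. The protocol therefore does not settle how AESI status and TEAE status fit together.

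**Scale.** SAP section 4: "The maximum potential Participants in VMALS-002-2b is 18, based on enrollment in VMALS-002-2". Each participant whose only AESI is of the affected kind changes incidence by 1/N.

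- Overall, N = 18: 1/18 = 5.6 percentage points (more if fewer enrol).
- Within an arm, size assumed because none is given: 1/12 = 8.3 points, 1/9 = 11.1 points, 1/6 = 16.7 points.

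How many participants would be affected cannot be derived from the documents.

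**The case against.** The best case on the other side is that the no-tabulation sentence is a timing rule. It follows a statement that adverse events are presented from the VMALS-002-2 screening visit onward. SAP 6.14.1 also says that screening events are recorded separately from TEAEs, so Listing 16.2.7.7 would hold pre-injection events. Every extension event comes after the injections. Table 14.3.1.9 is titled by AESI alone, whereas the other event tables are titled by TEAE or TESAE, so a programmer might simply select on the AESI flag. The SAP's list of tables is not legible in the public copy and may say more.

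This is a plausible account of intent, and it rules out saying that these AESIs are certainly barred. It does not remove the conflict: the sentence is not limited to pre-injection events, and the same section's definition excludes expected progression whatever its timing.

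It is also true that little would be hidden. The events stay in Listing 16.2.7.2, and SAP 6.3 sorts listings by treatment group, so with at most 18 participants the listing can be read by arm. The ALSFRS-R bulbar subscore, dynamometry, slow vital capacity and all-cause mortality are summarised by arm with no expectedness filter. What would be missing is the tabulated incidence, which is the stated primary endpoint.

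A reader might infer that most AESIs would be lost, because 15 of 18 participants in the sponsor's earlier ALS study died within 36 months (1 before the 9-month visit, 14 after it; protocol 2.2.6.1), all of respiratory failure associated with ALS. The documents do not support that step. Those deaths span 36 months, only one came before the 9-month visit, and they give neither an AESI rate for Day 180 to Day 365 nor any indication of how investigators judge expectedness.

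**Conclusion.** The stated rules conflict, and followed literally they can exclude required AESIs from the only AESI table named for a primary endpoint. The exposure is mainly bulbar signs, with some weakness events; pneumonia and aspiration are much less exposed. Whether an event is excluded depends on whether the site and the programmer apply the timing wording or the progression exclusion, so it may vary from site to site.

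The size is 5.6 percentage points of overall incidence per affected participant if all 18 enrol, and 8.3 to 16.7 points within an arm under the assumption of 6 to 12 per arm. No total effect can be given. Nothing suggests a bias in a particular direction between arms, and no hypothesis test is affected. This should be settled before database lock because it determines what the primary table counts.

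**What to change.** Two changes to the SAP text:

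- **6.14.1.** Add to the no-tabulation sentence an exception for AESIs with onset after the first VMALS-002-2 injection.
- **6.14.1.4.** State that Table 14.3.1.9 counts every event recorded as an AESI, whatever its TEAE status, for the same analysis periods as the TEAE tables, with one row giving how many were also TEAEs. Those periods need reconciling first: 6.14.1 plans TEAE tables for two sets (onset from extension consent, and both studies together), whereas 6.14.1.4 says that TEAEs starting before extension consent will not be tabulated.

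The protocol passages on serious AESIs (8.3.4) and on events that cannot be TESAEs (10.2.2) should be reconciled at the same time.

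The cost is a few sentences and one table row. No new data are needed, because the protocol already requires AESI recording. The downside is that reported AESI incidence may be higher; the extra row lets a reader see both counts.

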6.14.1.3 Adverse Events of Special Interests (AESI)

There are 3 main categories of AESIs as presented below:

- a) considered to be related to the angiogenesis potential of Engensis
- b) other medical problems in this patient population
- c) COVID-19 infections occurring in Participants during the study

AESI Considered Related to Angiogenesis

Atherosclerosis

Hyperplasia of the vasa vasorum in the early stages of atherosclerosis is independent of angiogenesis, but the intimal neovascularization that follows the hyperplasia of the vasa vasorum is angiogenesis-dependent. Angiogenesis increases oxygen and nutrients to the artery wall and supports initial plaque growth. Once the atherosclerotic plaque develops, intimal angiogenesis is thought to contribute to characteristics of an unstable plaque, plaque hemorrhage, and plaque rupture. Therefore, diagnoses suggestive of recent coronary artery disease since Baseline will be evaluated as AESIs.

QMD Ref: Worldwide-TMP-ST-005-7.0 Effective: 12Aug2019	Governing QMD: Worldwide-SOP-ST-001
Confidentiality Statement	

This document is the property of Worldwide Clinical Trials Inc. and may not be duplicated, copied, altered or removed from company without prior approval from Worldwide Quality Assurance or in compliance with Worldwide Standard Operating Procedures.

Worldwide Clinical Trials Controlled Quality Management Document			
 WORLDWIDE CLINICAL TRIALS	Sponsor:	Helixmith Co., Ltd.	
	Protocol Number:	VMALS-002-2b	
STATISTICAL ANALYSIS PLAN. PHASE 2-3-4			

Cancer

Angiogenesis plays an important role in the proliferation and metastatic spread of cancer as these processes are dependent on an adequate supply of oxygen and nutrients and removal of waste products. All types of cancer reported during the study will be deemed to be AESIs.

Other Medical Problems in ALS Patients

- Pulmonary Medical Problems: Because patients with ALS are at an increased risk to develop pulmonary medial problems such as aspiration of food or liquids, pneumonia, and respiratory arrest, all events of this type that occur during the study will be considered AESIs.
- Progressive Muscle Weakness: Because some patients with ALS may develop rapidly progressive muscle weakness that results in loss of ability to care for self, decubitus ulcers, or weight loss due to impaired deglutition, all events of this type that occur during the study will be considered AESIs.
- Bulbar Disease: Participants may develop bulbar disease or worsening on bulbar disease during the study, manifested as challenges with dysarthria, facial weakness, impaired tongue pulsion or palate elevation, and impaired mastication and swallowing; all of these types of events that occur during the study will be considered AESIs.

COVID-19 Infections

A diagnosis of COVID-19 infection occurring in participants will be recorded as an AESI and their disposition during the trial following the diagnosis of the COVID-19 infection will be tracked.

6.14.1.4 Outputs planned for Adverse Events

TEAEs with start date and time before date and time of the Informed Consent for VMALS002-2B will be presented in a separate listing and will not be tabulated.

The following tables will be presented:

- Summary of TEAEs (Table 14.3.1.1)
- TEAEs by System Organ Class and Preferred Term (Table 14.3.1.2)
- TESAEs by System Organ Class and Preferred Term (Table 14.3.1.3)
- TEAEs by System Organ Class and Preferred Term and Maximum Severity (Table 14.3.1.4)

QMD Ref: Worldwide-TMP-ST-005-7.0 Effective: 12Aug2019	Governing QMD: Worldwide-SOP-ST-001
Confidentiality Statement	

This document is the property of Worldwide Clinical Trials Inc. and may not be duplicated, copied, altered or removed from company without prior approval from Worldwide Quality Assurance or in compliance with Worldwide Standard Operating Procedures.

Worldwide Clinical Trials Controlled Quality Management Document			
 WORLDWIDE CLINICAL TRIALS	Sponsor:	Helixmith Co., Ltd.	
	Protocol Number:	VMALS-002-2b	
STATISTICAL ANALYSIS PLAN. PHASE 2-3-4			

- TEAEs by System Organ Class and Preferred Term and Maximum Relationship (Table 14.3.1.5)
- TESAEs by System Organ Class and Preferred Term and Maximum Severity (Table 14.3.1.6)
- TESAEs by System Organ Class and Preferred Term and Maximum Relationship (Table 14.3.1.7)
- Incidence of Clinically Significant Laboratory Values (Table 14.3.1.8)
- AESIs by System Organ Class and Preferred Term (Table 14.3.1.9)

The following listings will be provided:

- All TEAEs (Listing 16.2.7.1)
- AESIs (Listing 16.2.7.2)
- TESAEs (Listing 16.2.7.3)
- TEAEs leading to study discontinuation (Listing 16.2.7.4)
- TEAEs related to study medication (Listing 16.2.7.5)
- TESAEs leading to death (Listing 16.2.7.6)
- AEs that registered as not TEAEs (Listing 16.2.7.7)

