6.2.4 Conventions for Missing and Partial Dates

All rules explained below for partial / missing dates will be followed unless contradicted by any other data recorded on the electronic Case Report Form (eCRF).

All dates presented in the individual subject listings will be as recorded on the eCRF (i.e., not completed as per the below rules).

6.2.5 Missing / Partial Start / Stop Date of Adverse Events (AE) and Concomitant Medications

Missing and partial start and stop dates will be imputed for analysis purposes as follows.

Partial or missing stop date will be imputed as follows:

If the stop date is completely missing and the event has resolved, or the subject has stopped taking the concomitant medication, the stop date will be imputed as the date of the subject’s last clinic visit in the study.

- If only the year is known, the stop date will be imputed as “31-Dec” of that year or as the date of the subject’s last clinic visit in the study if in the same year.
- If the month and year are known, the stop date will be imputed as the last day of that month unless the stop date corresponds to the same month as the subject’s last clinic visit in which case the date of subject’s last clinic visit in the study will be used instead.

Missing start date will be imputed as follows:

- If the stop date occurs on or after the start of study drug or the event / concomitant medication is ongoing, the start date will be imputed as the date of the first dose of study drug.

QMD Ref: Worldwide-TMP-ST-005-7.0 Effective: 12Aug2019	Governing QMD: Worldwide-SOP-ST-001
Confidentiality Statement	

This document is the property of Worldwide Clinical Trials Inc. and may not be duplicated, copied, altered or removed from company without prior approval from Worldwide Quality Assurance or in compliance with Worldwide Standard Operating Procedures.

Worldwide Clinical Trials Controlled Quality Management Document			
 WORLDWIDE CLINICAL TRIALS	Sponsor:	Helixmith Co., Ltd.	
Protocol Number:			VMALS-002-2b
STATISTICAL ANALYSIS PLAN. PHASE 2-3-4			

- If the stop date occurs before the start of study drug, the start date of the event / concomitant medication will be imputed as the subject's screening date or the stop date of the event / concomitant medication whichever is earlier.

Partial start date (year present, but month and day missing)

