- If the stop date occurs on or after the start of study drug or the event / concomitant medication is ongoing, and the year is the same as the year of first dosing, the start date will be imputed as "01-Jan" of the same year or the date of the first dose of study drug whichever is the latest. If the year is different from the year of first dosing "01-Jan" will be used.
- If the stop date occurs before the start of study drug, the start date of the event / concomitant medication will be imputed as the "01-Jan" of the same year.

Partial start date (month and year present, but day missing)

- If the stop date occurs on or after the start of study drug or the event / concomitant medication is ongoing, the start date will be imputed as the first day of the same month and year unless this partial start date is in the same month as the first dose of study drug in which case, the date of first dose of study drug will be used.
- If the stop date occurs before the start of study drug, the start date will be imputed as the first day of the month and year of the partial stop date.

If the start time is missing it will be imputed only in the case where the start date of the concomitant medication / event corresponds to the date of the first dose of study drug. The time will be imputed as the same time as the first dose of study drug. In all other cases the time will not be imputed.

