6.15.6 Time to tracheostomy

Time to tracheostomy will be presented with descriptive statistics and corresponding survival curves using Kaplan- Meier analysis (Table 14.6.8, Listing 16.2.9.8).

SAS code example for Kaplan-Meier analysis:

```
proc lifetest data=DATAIN method = km;
  time AVAL*CNSR(1);
  strata TRT01PN / test = logrank;
run;
```

DATAIN – source dataset

AVAL – time to event

CNSR – flag for censoring, if CNSR=1 then the corresponding value of AVAL is a censored value and not an observed event

TRT01PN – treatment group

Analysis will be performed on data combined for core study the Study VMALS-002-2 (Screening, Day 0 pre-dose, Day 30, Day 60 pre-dose, Day 84, Day 120 pre-dose, Day 144 and Day 180) and for this extension study the Study VMALS-002-2b (Day 240, Day 300, Day 365/ET4).

QMD Ref: Worldwide-TMP-ST-005-7.0 Effective: 12Aug2019	Governing QMD: Worldwide-SOP-ST-001
Confidentiality Statement	

This document is the property of Worldwide Clinical Trials Inc. and may not be duplicated, copied, altered or removed from company without prior approval from Worldwide Quality Assurance or in compliance with Worldwide Standard Operating Procedures.

Worldwide Clinical Trials Controlled Quality Management Document			
 WORLDWIDE CLINICAL TRIALS	Sponsor:	Helixmith Co., Ltd.	
	Protocol Number:	VMALS-002-2b	
STATISTICAL ANALYSIS PLAN. PHASE 2-3-4			

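### SAP 6.14.1 and 6.14.1.4 disagree on whether TEAEs before extension consent are tabulated, and the start-date imputation in 6.2.5 ignores the consent date, so some incompletely dated extension TEAEs leave the extension tables

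*SAP*

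**What the plan says.** Incidence of TEAEs, TESAEs and AESIs, Engensis against Placebo, is a primary endpoint (SAP 3.1). Protocol 9.3.1 makes it descriptive, with no formal testing.

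**Which TEAEs are tabulated.** SAP 6.14.1 names two sets: "TEAEs started at date of signing of IC for this study or later and all TEAEs collected during both studies". SAP 6.14.1.4, which lists the outputs, opens by saying that TEAEs with a start "before date and time of the Informed Consent for VMALS002-2B will be presented in a separate listing and will not be tabulated". It then lists one series of tables (14.3.1.1 to 14.3.1.7 for TEAEs and TESAEs, 14.3.1.9 for AESIs) without saying which set each one uses. The cut is by date in 6.14.1 and by date and time in 6.14.1.4.

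**How incomplete onsets are filled (SAP 6.2.5), for events that are ongoing or stop on or after first dose:**
- Fully missing: "the start date will be imputed as the date of the first dose of study drug".
- Year only, same year as first dosing: 01-Jan "of the same year or the date of the first dose of study drug whichever is the latest". In any other year: 01-Jan.
- Month and year: "the start date will be imputed as the first day of the same month and year", except in the month of first dose, when the first-dose date is used.
- A missing start time is filled only on the first-dose date. "In all other cases the time will not be imputed".

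SAP 6.2.4 says that the date rules "will be followed unless contradicted by any other data recorded on the electronic Case Report Form (eCRF)". It does not say which data count as a contradiction.

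**The concern.** There are two separate defects.

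1. Read literally, the sentence in 6.14.1.4 rules out the both-study set that 6.14.1 calls for. Two programmers could deliver different outputs in good faith. If the 6.14.1.4 sentence prevails, this SAP gives no by-arm TEAE table running from first injection to Day 365. All dosing lies in the parent study: no drug is given in the extension, and the visit list in SAP 6.15.6 marks the pre-dose visits at Days 0, 60 and 120 ("Screening, Day 0 pre-dose, Day 30, Day 60 pre-dose, Day 84, Day 120 pre-dose, Day 144 and Day 180").

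2. The extension set is defined by the consent date, but no start-date rule in 6.2.5 uses that date. A TEAE that truly began in the extension can therefore be imputed to a date before consent. Under 6.14.1 it would still appear in the both-study set. Under 6.14.1.4 it would appear in no table.

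The differing cut also matters on the consent day. A TEAE on that day with no recorded time cannot be classified under the date-and-time rule, because its time is not imputed.

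**Working it through.** **Part 1: the two sections side by side.** A TEAE starting after the consent day is tabulated under both. A TEAE starting before the consent day is tabulated under 6.14.1 (both-study set) and not under 6.14.1.4. A TEAE on the consent day is in the extension set under 6.14.1; under 6.14.1.4 its place depends on a clock time that may be missing. The open questions are therefore the both-study tables and consent-day events.

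**Part 2: share of true extension TEAEs imputed before consent.** The plan states no figure to reproduce, so the rules were applied directly.

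Inputs from the documents: the rules of SAP 6.2.5; first dose is in VMALS-002-2; consent may be signed before, on or after Day 180 (Protocol 5.1) but before any study procedure (Protocol 10.1.1.2), so at the latest at the Day 240 visit; visit windows are ±7 days (Protocol 1.3).

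Assumptions: first-dose dates spread evenly over 365 days; onset equally likely on each day from consent to last visit; event ongoing or stopped on or after first dose; the eCRF-contradiction clause not used; Day 150 as the earliest consent.

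For each pair of first-dose date and onset day, the onset was imputed and compared with consent:

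share = (pairs with imputed date before consent) / (all pairs)

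With consent at Day 180 and end at Day 365 there are 365 × 186 = 67,890 pairs:
- fully missing: 67,890/67,890 = 100%
- year only: 50,499/67,890 = 74.4%
- month and year: 5,373/67,890 = 7.9%

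| Consent day | End day | Year only | Month and year |
|---|---|---|---|
| 150 | 372 | 69.3% | 6.6% |
| 150 | 365 | 70.3% | 6.8% |
| 180 | 365 | 74.4% | 7.9% |
| 240 | 365 | 82.6% | 11.7% |
| 247 | 358 | 84.5% | 13.1% |

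The first and last rows use the limits of the visit windows. Fully missing onsets give 100% in every row. These are averages: for a single first-dose date with consent at Day 180, the share runs from 0% to 100% (year only) and from 0% to 16% (month and year). In no case was the imputed date later than the true onset.

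**Example (assumed dates).** First injection 11-Sep-2021, consent 10-Mar-2022 (Day 180):
- missing → 11-Sep-2021, out
- 2022 → 01-Jan-2022, out
- Mar-2022 → 01-Mar-2022, out
- Jun-2022 → 01-Jun-2022, in

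**Effect on a table row.** A back-dated event changes a participant's overall, SOC or PT incidence only if it is that participant's sole event in the row. The row then falls by 100/N points: 100/18 = 5.6 in the overall column at the maximum of 18 participants, and more within an arm. In the maximum-severity and maximum-relationship tables (14.3.1.4 to 14.3.1.7), losing a participant's severe event while a mild one of the same PT remains lowers the severe row and raises the mild row.

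**The case against.** The sentence in 6.14.1.4 may have been meant only for the extension-period tables. The table index in SAP section 11 cannot be read in this copy and may already assign tables to each set and name the separate listing. Both points stand, which makes Part 1 a repair of wording and a check of the index.

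The eCRF clause in 6.2.4, the closing of all queries before lock (Protocol 10.1.6.5) and the full AE listings limit Part 2. This also stands in part. The clause could rescue some events, but it does not mention consent and gives no test for when it applies.

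A reader might infer that about half of the safety data is lost, since 180/365 = 49% of follow-up precedes a Day 180 consent. The documents do not support that. The figure is a share of time and not of events, TEAEs after the consent day are tabulated under either section, Protocol 8.3.1 starts TEAE collection for this study at extension consent, and the protocol does not expressly require both-study tables.

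A reader might also infer that the imputation can only lower reported incidence. That holds for overall, SOC and PT incidence. It fails for the lower-category rows of the maximum-severity and maximum-relationship tables.

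**Conclusion.** Both parts hold and should be fixed before lock. The two SAP sections conflict as written, and the imputation does not serve the consent cut that defines the extension set.

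Given an incomplete onset, the share moved out of the extension set is 100% if fully missing, 74% on average if year only and 7.9% on average if month and year, with consent at Day 180. Across consent from Day 150 to Day 247 and the final visit window, the averages are 69-85% and 6.6-13.1%. They rest on evenly spread dates and on the eCRF clause not being used. With at most 18 participants, first-dose dates need not average out, so the spread by first-dose date matters more than the mean.

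The documents give no rate of incomplete onsets. The total effect is therefore unknown, and probably small. No hypothesis test is affected.

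**What to change.** Before database lock:

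(a) Limit the sentence in 6.14.1.4 to the extension-period tables, or delete it. Keep the two-set rule of 6.14.1. Confirm that the section 11 index assigns tables to each set and includes the separate listing of pre-consent TEAEs.

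(b) Cut by consent date in both sections, since missing times are not imputed.

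(c) Only for assigning TEAEs to the extension set, impute an incomplete onset as the later of the earliest date compatible with the recorded parts and the extension consent date. Apply this when the recorded parts and stop date allow an onset on or after consent and the event was first reported in the extension eCRF. For consent before Day 180, include events first reported in the parent eCRF at a visit on or after consent. Otherwise keep the present rule. Footnote the number of events so assigned.

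(d) State that this rule serves set assignment only, so that it does not conflict with Protocol 9.3.1, which rules out imputing missing values in the safety analyses.

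The cost is SAP wording and some programming, including identifying in which study and at which visit an event was first reported. A few incompletely dated parent-study events may be counted in the extension set, so its incidence may look slightly higher. A date cut also counts consent-day events that began before signing.
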